## **6.2. Treatment Compliance**

An adequate record of receipt, distribution, and return of all study drugs must be documented on a Drug Accountability Form.

Study drug will be dispensed to subjects, and the pills bottles returned to LCI Clinical Trials staff according to LCI standard operating procedures. IDS Pharmacy staff will report the number of pills in the bottles returned to LCI Clinical Trials. The number

of pills the subjects take per cycle will be derived from these pill counts rather than reported by the subjects on a pill diary.

Subject compliance with the treatment and protocol includes willingness to comply with all aspects of the protocol, and to have blood collected for all safety evaluations. At the discretion of the Sponsor-Investigator, a subject may be discontinued from the trial for non-compliance with follow-up visits or study drug.

### **6.3. Duration of Therapy**

In the absence of treatment delays due to adverse event(s), treatment will continue until one of the following criteria applies:

- Disease progression,
- Intercurrent illness that prevents further administration of treatment
- Unacceptable adverse event(s),
- Subject decides to withdraw from the study, or
- General or specific changes in the subject's condition render the subject unacceptable for further treatment in the judgment of the Investigator.

### **6.4. Drug Accountability**

All study drugs will be stored at the investigational pharmacy in accordance with Good Clinical Practice (GCP) and Good Manufacturing Practices (GMP) requirements and will be inaccessible to unauthorized personnel.

An adequate record of receipt, distribution, and destruction of all study drugs must be documented on a Drug Accountability Form. The Investigator, or a responsible party designated by the Investigator, will maintain a careful record of the inventory using the Drug Accountability Form.

### **6.5. Destruction**

At the end of the study, unused supplies of regorafenib will be destroyed according to LCI IDS pharmacy policies. Destruction will be documented in the Drug Accountability Form and sent to Bayer at the following address:

Email: [[contact]](mailto:[contact])

Mail: [name]

Bayer HealthCare Pharmaceuticals

[name]

[name]

[contact]

## 7. TREATMENT-RELATED ADVERSE EVENTS

### 7.1. Adverse Events Related to Regorafenib

Based on data studies with regorafenib and from current knowledge of the pharmacological properties of other small molecule tyrosine kinase inhibitors in this drug class, as soon as there is reasonable suspicion of any of the AEs in the following sections, the Investigator should immediately notify the appropriate agencies as outlined in Section 9.

### 7.2. Prevention and Management of Adverse Events

#### 7.2.1. Dose Modifications for Adverse Events

**The starting dose of regorafenib is 120 mg once daily (starting dose level -1) but with a planned dose escalation (to dose level 0) with cycle 2 if less than grade 2 clinically significant toxicity (per the Investigator) is experienced (see section 6.1.1.2).** Study medication will be administered on a 21 days on/7 days off schedule (3 weeks out of every 4). Doses will be delayed or reduced for clinically significant hematologic and non-hematologic toxicities that are related to protocol therapy according to the guidelines shown in the Dose Delays/Dose Modifications table that follows. Dose modifications will follow predefined dose levels. Dose adjustments for hematologic toxicity are based on the blood counts obtained in preparation for the day of treatment.

The modifications of regorafenib will follow the following predefined dose levels:		
Dose level 0	160 mg po daily	Four 40-mg tablets of regorafenib
Dose level -1	120 mg po daily	Three 40-mg tablets of regorafenib
Dose level -2	80 mg po daily	Two 40-mg tablets of regorafenib

If a subject experiences more than one toxicity, dose reduction should be according to the toxicity with the highest grade. In the case of two or more toxicities of the same grade, the Investigator may dose reduce according to that deemed most causally related to study treatments. If treatment is held for more than 4 weeks due to toxicity or if dose reductions beyond dose level -2 are necessary, then treatment will be permanently discontinued.

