#### **6.1.1.2. Regorafenib Dose Escalation (Cycle 2 and Subsequent Cycles)**

After the first cycle of therapy on study and at the start of cycle 2, subjects who have no worse than grade 1 toxicity (CTCAE v4) will have a dose escalation up to 160 mg daily, taken for 21 days followed by 7 days off. Subjects with clinically significant grade 2 or higher toxicity considered possibly, probably, or definitely related to regorafenib, OR, in the Investigator's opinion, may adversely impact the safety of the subject will not have a dose escalation (excluding alopecia, non-refractory nausea/vomiting, non-refractory hypersensitivity and nonclinical and asymptomatic laboratory abnormalities). Subjects who undergo dose escalation up to 160 mg will take four 40 mg regorafenib oral tablets each morning as per section 6.1.1.1. Dose reduction for toxicity will follow standard protocol guidelines (see section 7.2).

Dose escalation by 1 level (i.e. from dose level -1 to dose level 0, or from dose level -2 to dose level -1) can be considered as above at the treating Investigator's discretion at the beginning of each subsequent 28 day cycle for any subject who has no worse than clinically-significant grade 1 toxicity. Doses beyond 160 mg are not permitted. Dose reduction for toxicity will follow standard protocol guidelines, whether or not dose escalation had previously occurred.

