#### **7.2.4. Grading and Dose Adjustments for Hypertension**

Hypertension is a known AE associated with regorafenib treatment. Subject will have their blood pressure measured at least weekly at the study site during the first 6 weeks of treatment. If additional blood pressure measurements are done outside the study site, and the blood pressure is > 140 mm Hg systolic or > 90 mm Hg diastolic (NCI CTCAE v4.0), then the subject must contact study personnel. The management of hypertension, including the choice of antihypertensive medication, will be performed according to local standards and to the usual practice of the Investigator. Every effort should be made to control blood pressure by medical means other than study drug dose modification. If necessary, Table 7.4 outlines suggested dose reductions.

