**Table 7.4: Management of Treatment-Emergent Hypertension**

Grade (CTCAE v4.0)	Antihypertensive Therapy	Regorafenib Dosing
1  Prehypertension (systolic BP 120 - 139 mmHg or diastolic BP 80 - 89 mmHg)	None	
 
Continue regorafenib
 
Consider increasing blood pressure (BP) monitoring
 

2  Systolic BP 140 - 159 mmHg or diastolic BP 90 - 99 mmHg, OR Symptomatic increase by > 20 mmHg (diastolic) if previously within normal limits	
 
Treat with the aim to achieve diastolic BP < 90 mm Hg:
 
If BP previously within normal limits, start anti-hypertensive monotherapy
 
If subject already on anti-hypertensive medication, titrate up the dose.
 
	
 
Continue regorafenib
 
If symptomatic, hold regorafenib until symptoms resolve AND diastolic BP ≤ 90 mm Hga. When regorafenib is restarted, continue at the same dose level.
 

3  Systolic BP ≥ 160 mmHg or diastolic BP ≥ 100 mmHg OR More than one drug or more intensive therapy than previously used indicated	
Treat with the aim to achieve diastolic BP ≤ 90 mm Hg: Start anti-hypertensive medication
 
AND/OR Increase current anti-hypertensive medication
 
AND/OR Add additional anti-hypertensive medications.
	
 
Hold regorafenib until diastolic BP ≤ 90 mm Hg, and if symptomatic, until symptoms resolve.a
 
When regorafenib is restarted, continue at the same dose level.
 
If BP is not controlled with the addition of new or more intensive therapy, reduce by 1 dose level.b
 
If Grade 3 hypertension recurs despite dose reduction and antihypertensive therapy, reduce another dose level.c
 

4  Life-threatening consequences (eg, malignant hypertension, transient or permanent neurologic deficit, hypertensive crisis)	Per institutional guidelines	Discontinue therapy

a. Subjects requiring a delay of >4 weeks should go off protocol therapy

b. If BP remains controlled for at least one cycle, dose re-escalation permitted per Investigator's discretion.

c. Subjects requiring $\geq 2$ dose reductions should go off protocol therapy.
--

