### 7.2.5. Dose Adjustments for Liver Function Test Abnormalities

For subjects with observed worsening of serum liver tests considered related to regorafenib (i.e. where no alternative cause is evident, such as post-hepatic cholestasis or disease progression), the dose modification and monitoring advice in Table 7.5 should be followed.

Regorafenib is a UGT1A1 inhibitor. Mild, indirect (unconjugated) hyperbilirubinemia may occur in subjects with Gilbert's syndrome.

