**Table 7.5: Dose modifications/interruption for ALT and/or AST and/or Total Bilirubin increases related to study drug**

Observed elevations	1 st Occurrence	Restart	Re-occurrence
baseline G0 $\rightarrow$ G1 or baseline G1 $\rightarrow$ G2	Treat on time and check AST, ALT and bilirubin 2x/week for 2 weeks followed by weekly assessments for at least 4 weeks.		Treat on time and check AST, ALT and bilirubin 2x/week for 2 weeks followed by weekly assessments for at least 4 weeks.
baseline G0 $\rightarrow$ G2	Delay until $\leq$ G1 and check AST, ALT, bilirubin 2x/week.	Reduce 1 dose level and check AST, ALT, bilirubin 2x/week for 2 weeks followed by weekly assessments for at least 4 weeks. a	Discontinue

Baseline any grade → G3	
Delay until <math>\leq</math> G1 if baseline was G0 or G1 OR until G2 if baseline was G2.
 
Check AST, ALT, bilirubin 2x/week.
 
If ALT or AST <math>> 8 \times</math> ULN with a concomitant rise in bilirubin (of any degree) compared to previous bilirubin values, consider permanent discontinuation at the first occurrence.
	
Reduce 1 dose level and check AST, ALT, bilirubin 2x/week for 2 weeks followed by weekly assessments for at least 4 weeks.a
	Discontinue
Before regorafenib initiation and during the first 2 cycles of treatment, ALT, AST and bilirubin must be monitored at least every 2 weeks.			
a: If toxicity returns to $\leq$ Grade 1 after dose reduction, dose re-escalation is permitted at the discretion of the treating Investigator per Section 6.1.1.2 for first occurrence only.			

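### Section 7.2.1 ranks concurrent toxicities by grade, but grade does not order strictness across the dose tables, so read literally it can bypass a liver dose reduction

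*Combined protocol and SAP*

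**What the plan says.** Section 7.2.1 is the only place that deals with several toxicities at once: "If a subject experiences more than one toxicity, dose reduction should be according to the toxicity with the highest grade". For toxicities of equal grade it lets the investigator reduce according to the one judged most causally related to treatment. It also says that a reduction that would go below dose level -2 (80 mg) means permanent discontinuation.

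Hypertension and liver tests are then handled in separate tables:

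- **Table 7.4, Grade 3 hypertension.** The drug is held until diastolic pressure is 90 mm Hg or lower and any symptoms have resolved. Then: "When regorafenib is restarted, continue at the same dose level". A reduction comes only if control fails: "If BP is not controlled with the addition of new or more intensive therapy, reduce by 1 dose level". Section 7.2.4 introduces the table with: "If necessary, Table 7.4 outlines suggested dose reductions".
- **Table 7.5, liver tests.** For drug-related worsening, 7.2.5 says "the dose modification and monitoring advice in Table 7.5 should be followed". A first rise from baseline Grade 0 to Grade 2, or from any baseline grade to Grade 3, is delayed to recovery. At restart the instruction is "Reduce 1 dose level and check AST, ALT, bilirubin 2x/week for 2 weeks", followed by weekly checks. Recurrence means discontinuation. Footnote a adds that, once the toxicity has returned to Grade 1 or lower, "dose re-escalation is permitted at the discretion of the treating Investigator per Section 6.1.1.2 for first occurrence only".

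**The concern.** A highest-grade rule protects the subject only if a higher grade always brings an equal or stricter action. That is true within Table 7.1. It is not true across Tables 7.1 and 7.3 to 7.5, because a Grade 2 liver event can call for a reduction when a Grade 3 hypertension event calls for none. An investigator who applies 7.2.1 to the letter would then restart at the full previous dose after a drug-related liver signal, while a colleague who follows 7.2.5 would go down one level. On the literal reading, adding a second toxicity raises the restart dose above what the liver event alone would have given. Section 14.1 asks for strict adherence and section 4.2 foresees further sites, so the choice of reading should not be left to each investigator.

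**Working it through.** The plan states no figure for this point. The check sets the rules side by side and then sizes the gap.

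**1. Does grade order strictness within Table 7.1?** Grades 0 to 1: no reduction. Grade 2: no change. Grade 3: down one level. Grade 4: down one level, with discontinuation an option. The action never becomes milder as grade rises, so ranking by grade works there.

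**2. Does it order strictness across the tables?** Take a subject with controlled Grade 3 hypertension and a first drug-related liver rise from Grade 0 to Grade 2.

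| Route | Row selected | Levels down at restart |
|---|---|---|
| 7.2.1 read literally | Grade 3 hypertension, Table 7.4 | 0 |
| 7.2.5 | Grade 0 to Grade 2 liver rise, Table 7.5 | 1 |

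The equal-grade sentence does not apply, because the grades are 3 and 2.

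**3. Equal grades.** With controlled Grade 3 hypertension and a first drug-related Grade 3 liver rise, Table 7.5 calls for one level down. Under 7.2.1 the investigator may go by the event judged more causally related. If that is the hypertension, the result is again 0 levels down.

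**4. Size of the gap per 21-day dosing period** (dose levels from 7.2.1, schedule from 6.1.1.1):

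- From 160 mg: 160 × 21 = 3360 mg versus 120 × 21 = 2520 mg. The difference is 840 mg, and 840/3360 = 25.0%.
- From 120 mg: 120 × 21 = 2520 mg versus 80 × 21 = 1680 mg. The difference is 840 mg, and 840/2520 = 33.3%.
- From 80 mg: 80 × 21 = 1680 mg versus permanent discontinuation, because the next step would be below level -2.

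**5. Where the routes agree.** If the liver rise is from Grade 1 to Grade 2, Table 7.5 treats on time. If blood pressure is not controlled, Table 7.4 also goes down one level. Grade 4 hypertension means discontinuation under Table 7.4. None of these creates a conflict.

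**6. Hand-foot skin reaction.** A Grade 2 reaction that recurs or does not improve also restarts at a reduced level in Table 7.3. It is a weaker example: that table offers suggestions, and its footnote a allows more conservative management. No such footnote is attached to Table 7.4 or 7.5.

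**7. Frequency.** Section 2.2.2 gives Grade 3 or higher hypertension as 7% in the colorectal trial and 48.5% in the GIST trial, both at 160 mg; this trial starts at 120 mg. Those rates include Grade 4, where there is no conflict. Nothing in the documents gives the share who also have a first drug-related liver rise with controlled blood pressure, so no count can be derived.

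**The case against.** The best defence is that the sentence in 7.2.1 is about dose reduction. Controlled hypertension calls for none, so only the Table 7.5 reduction is due and nothing competes with it. Section 7.2.4 supports this by asking that blood pressure be managed by means other than dose changes where possible. This reading is reasonable and removes the conflict. The text does not compel it, however: what triggers the rule is more than one toxicity, not more than one reduction due.

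A second defence is that 7.2.1 refers to a single dose-modification table that follows, arguably Table 7.1, which excludes hypertension and ALT, AST and bilirubin. But the sentence stands in the general subsection, ahead of all the tables, and that reference does not clearly confine it.

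Third, the combination is narrow. It needs controlled Grade 3 hypertension and a first liver rise with no other evident cause, in a disease where biliary obstruction and liver metastases are common alternatives. For the Grade 2 case the liver baseline must also be Grade 0, whereas section 3.1 admits subjects with raised transaminases. This stands and limits the practical weight.

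A reader might go further and infer that the protocol gives no rule of precedence at all. The documents do not support that: the highest-grade sentence is itself such a rule. The fault is that it can point to the more lenient row, and that 7.2.5 does not say whether it gives way. Nor does the protocol forbid the liver reduction: 7.2.5 on its own directs it, and Table 7.4 is offered only as a suggestion.

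**Conclusion.** The point holds as a low-priority safety correction. On a literal reading, ranking by grade can bypass a one-level reduction that Table 7.5 calls for when the liver event occurs alone. The equal-grade sentence can do the same at Grade 3. On the reading that 7.2.1 chooses only among reductions that are due, there is no conflict.

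The consequence is one dose level, or continuation instead of stopping at 80 mg. It is bounded, because Table 7.5's delay, extra monitoring and discontinuation on recurrence apply in any case. A reduced dose may also be raised again at the investigator's discretion under footnote a and section 6.1.1.2, which allows this "at the beginning of each subsequent 28 day cycle".

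Probably very few subjects would be affected. A reader might be tempted to multiply the hypertension rates in section 2.2.2 by an assumed overlap and quote a number out of 32. The documents give no basis for the overlap, so no subject count should be claimed. The primary analysis of 16-week progression-free survival, its alpha and its power are not affected.

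**What to change.** Replace both the highest-grade and the equal-grade sentences in 7.2.1 with: *If a subject experiences more than one drug-related toxicity, each applicable table (7.1, 7.3, 7.4, 7.5) is followed and the most conservative required dose action applies; where a table only says an action may be considered, the Investigator decides.* The last clause matters because some rows of Tables 7.1 and 7.3 are worded as options.

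The cost is low: one sentence in place of two, with no new procedure or data. The downside is a dose one level lower, or discontinuation from 80 mg, in the few subjects affected, which is what Table 7.5 and 7.2.1 already require when the liver event occurs alone. Under section 14.1 a protocol modification needs the funder's agreement and, when necessary, IRB approval, so the change can be made at the next amendment.

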### 7.2.2. Dose Adjustments for Adverse Events (other than hand-foot-skin reaction, hypertension and liver function test abnormalities)

The following tables outline dose adjustments for toxicities related to study drug except hand-foot skin reaction, hypertension and liver function test abnormalities.

**Table 7.1: Recommended dose modification for toxicities except hand-foot-skin reaction, hypertension and ALT/AST/Total Bilirubin**

NCI-CTCAE v4.0 a	Dose Interruption	Dose Modification b	Dose for Subsequent Cycles
Grade 0-1	Treat on time	No change	Dose escalation or No change (see section 6.1.1.2)
Grade 2	Treat on time	No change	No change
Grade 3	Delay until $\leq$ Grade 2 c	Reduce by 1 dose level	If toxicity remains $<$ Grade 2, dose re-escalation can be considered at the discretion of the treating Investigator. If dose is re-escalated and toxicity ( $\geq$ Grade 3) recurs, institute permanent dose reduction.
Grade 4	Delay until $\leq$ Grade 2 c	Reduce by 1 dose level.  Permanent discontinuation can be considered at treating Investigator's discretion.	

a. NCI-CTCAE = National Cancer Institute - Common Terminology Criteria for Adverse Events, version 4.0  
 b. Excludes alopecia, non-refractory nausea/vomiting, non-refractory hypersensitivity and nonclinical and asymptomatic laboratory abnormalities.  
 c. If no recovery after a 4 week delay\*, treatment should be permanently discontinued

The table above outlines dose adjustments for hematologic and non-hematologic toxicities related to regorafenib except HFSR and hypertension. In addition to these recommended dose modifications, subjects who develop diarrhea, mucositis, anorexia or other events predisposing to fluid loss or inadequate fluid intake should be carefully monitored and rehydrated as clinically necessary. This is in order to minimize the risk of postural hypotension and renal failure.

### 7.2.3. Grading and Dose Adjustments for Hand-Foot-Skin Reaction (HSFR)

Table 7.2: Grading for Hand-Foot-Skin-Reaction			
	Grade 1	Grade 2	Grade 3
NCI-CTCAE v4.0 Palmar-plantar erythrodysesthesia syndromea	Minimal skin changes or dermatitis (e.g., erythema, edema, or hyperkeratosis) without pain	Skin changes (e.g., peeling, blisters bleeding, edema, or hyperkeratosis) with pain	Severe skin changes (e.g., peeling, blisters, bleeding, edema, or hyperkeratosis) with pain
Further description / examples of skin changes	Numbness, dysesthesia / paresthesia tingling, painless swelling, or erythema of the hands and/or feet	Painful erythema and swelling of the hands and/or feet	Moist desquamation, ulceration, blistering, or severe pain of the hands and/or feet
Effect on activities	Does not disrupt normal activities	Limiting instrumental activities of daily life (e.g., preparing meals, shopping for groceries or clothes, using the telephone, managing money)	Limiting self-care activities of daily life (e.g., bathing, dressing and undressing, feeding self, using the toilet, taking medications) and not bedridden
a. Palmer-plantar erythrodysesthesia syndrome is a disorder characterized by redness, marked discomfort, swelling, and tingling in the palms of hands or the soles of the feet.			

**Table 7.3 Recommended dose modification for hand-foot-skin reactiona**

Grade of event (NCI-CTCAE v4.0)	Occurrence	Suggested Dose Modification
Grade 1	Any	Maintain dose level and immediately institute supportive measures for symptomatic relief
Grade 2	1 st occurrence	Consider decreasing dose by one dose level and immediately institute supportive measures. If no improvement, interrupt therapy for a minimum of 7 days, until toxicity resolves to Grade 0-1 b, c
	No improvement within 7 days or 2 nd occurrence	Interrupt therapy until toxicity resolves to Grade 0-1. c When resuming treatment, treat at reduced dose level b
	3 rd occurrence	Interrupt therapy until toxicity resolves to Grade 0-1. c When resuming treatment, decrease dose by one dose level. b, d
	4 th occurrence	Discontinue therapy
Grade 3	1 st occurrence	Institute supportive measures immediately. Interrupt therapy for a minimum of 7 days until toxicity resolves to Grade 0-1. c When resuming treatment, decrease dose by one dose level. b, d
	2 nd occurrence	Institute supportive measures immediately. Interrupt therapy for a minimum of 7 days until toxicity resolves to Grade 0-1. c When resuming treatment, decrease dose by one additional dose level b, d
	3 rd occurrence	Discontinue treatment permanently.

a. More conservative management is allowed if judged medically appropriate by the Investigator.  
b. If toxicity returns to Grade 0-1 after dose reduction, dose re-escalation is permitted at the discretion of the Investigator if subject has completed one cycle at reduced dose without recurrence of event.  
c. If there is no recovery after a 4-week delay, treatment with regorafenib will be discontinued permanently.  
d. Subjects requiring > 2 dose reductions should go off protocol therapy.  
e. The maximum daily dose is 160 mg.

At first occurrence of HFSR, independent of grade, prompt institution of supportive measures such as topical emollients, low potency steroids, or urea-containing creams should be administered.

Recommended prevention/management strategies for skin toxicities consistent with HFSR are summarized below:

